#### 3.1 Patient Recruitment

Eight Northern Regional Endoscopy Group (NREG- with a strong track record in delivering large endoscopy trials) units and Kettering General Hospital NHS Trust will recruit patients. Sites from NREG include: South Tyneside District Hospital, Freeman Hospital, Northumbria NHS Trust, Sunderland Royal Hospital, James Cook University Hospital, County Durham and Darlington Foundation Trust, Leeds Teaching Hospitals NHS Trust and North Tees University Hospitals.

Approximately 1430 patients undergoing colonoscopy as part of the BCSP or symptomatic service (most commonly patients with iron deficiency anaemia, altered bowel habit, weight loss and rectal bleeding) will be identified from endoscopy lists and recruited by a member of the research team. The final target number of participants will be refined after the first 100 participants have been recruited however this is not expected to vary significantly. Methodology by Peduzzi et al is used to calculate the minimum number of cases required to measure all variables and develop the risk model. Sample size N=10\*(k/p), where k is the number of covariates to be investigated in the model (n=15) and p the smallest of the proportions of positive or negative cases (=ADR=0.15). For non-BCSP population, ADR is around 15%; 1000 from this population are required. Minimum ADR within the BCSP is 35%; 430 cases are required to adequately power and build the model. This will allow resolution of small scale effects of covariates on risk prediction. Using Demidenko's method, the sample size needed for logistic regression with 80% power and 5% level of significance is N=8V/β2, where  $\beta$  is the natural log of the

odds ratio and V is logistic model variance due to covariates. This formula can be rearranged to determine the minimum odds ratio that can be detected at a sample size of 2000 with sufficient power. Assuming a moderate standard error in the regression (se=0.125), and calculating V from the standard error (V=(se\*vN)2) the study will have sufficient statistical power to detect an effect with a small effect size with an odds ratio of 1.42. The final sample size will be refined using data from the first 100 participants and observed effect size(s), however, the total number of recruits will not exceed 2000.

All potential participants will be sent or given a patient information leaflet about the study when their colonoscopy paperwork is sent or given to them, allowing adequate time to read the information leaflet (at least 24 hours) before consenting to the study. On attending the endoscopy unit for their procedure, they will be approached by a member of the research team and given the opportunity to discuss the study. Written consent will be obtained from those wishing to participate in the study. Specific consent to inform the participant's General Practitioner (GP) of participation will be obtained. Both non-consenting and consenting patients will receive their colonoscopy according to standard routine practice. Study participants will also undergo a health questionnaire, height and weight measurements and blood tests. In addition, intra-procedure data will be collected by a member of the research team onto a case report form (CRF). Any polyps detected and removed will be followed up, and histological diagnosis recorded post procedure by the research team. No additional follow-up or alteration of subsequent care is required for this study. The study will not affect the timing of outpatient appointments or results. Data will be collated and analysed by the research team. Adverse events will be classified by the chief investigators team.

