Approximately 400,000 colonoscopies are performed each year within the NHS for the investigation of gastrointestinal symptoms, including altered bowel habit, rectal bleeding and iron deficiency anaemia. Adenoma detection rate (ADR), defined as the number of procedures in which at least one adenoma is detected, is a widely accepted quality measure. A recent colonoscopy audit demonstrated an average polyp detection rate of 32.1%; however, ADR is variable between colonoscopists. A recent study estimated mean ADR of 15.9%. Patients found to have adenomas receive surveillance procedures, however these are currently based entirely upon number and size of adenomas with no patient factors considered. The NHS Bowel Cancer Screening Programme (BCSP)

invites all individuals aged 60-74 to undertake biennial faecal occult blood testing (FOBt). Screening is currently population based and non-targeted. Patients with a positive FOBt are invited for colonoscopy. The national Bowelscope screening programme is currently being rolled out in England and Wales, with the Lead applicants unit the first nationally to deliver this programme. All individuals aged 55 are invited for a single flexible sigmoidoscopy and adenoma clearance. Those deemed to be high risk undergo completion colonoscopy.

The mean ADR per colonoscopist within the FOBt BCSP is 46.5%, which is much higher than the symptomatic population due to the targeted nature of the programme. The BCSP has demonstrated a significant stage shift in CRC diagnosed. At present, the FOBt based screening programme is not providing protection against right sided CRC. A trial within the Scottish screening programme demonstrated that screening was an effective environment for interventions to alter patient behaviour.

In summary, although a study in an Asian population suggested an association between NAFLD and colorectal neoplasia, this has not been repeated in a Western population. It is important that the association is explored in a Western population but using non-invasive markers of liver disease and a wider range of colorectal neoplasia risk factors. This will allow development of a model to predict colorectal adenoma risk guiding screening and surveillance.

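### The detectable odds ratio of 1.42 does not depend on the sample size: it restates an unsourced standard error of 0.125, and nothing is shown for the planned 1430 patients

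*Protocol*

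**What the plan says.** All of this is in Protocol section 3.1, Patient Recruitment.

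- **Planned size.** "Approximately 1430 patients undergoing colonoscopy as part of the BCSP or symptomatic service" are to be recruited. This is the sum of two events-per-variable calculations with 15 covariates: "For non-BCSP population, ADR is around 15%; 1000 from this population are required" and "Minimum ADR within the BCSP is 35%; 430 cases are required to adequately power and build the model". The target is to be refined after the first 100 participants, but little change is expected.
- **Ceiling.** "the total number of recruits will not exceed 2000".
- **Detectable effect.** For 80% power and 5% significance the section gives N = 8V/β², where β is the log odds ratio. It then says: "This formula can be rearranged to determine the minimum odds ratio that can be detected at a sample size of 2000 with sufficient power". The input is "Assuming a moderate standard error in the regression (se=0.125), and calculating V from the standard error", with V = (se × √N)². The conclusion is that "the study will have sufficient statistical power to detect an effect with a small effect size with an odds ratio of 1.42".

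The standard error is described only as moderate. No predictor, exposure share, detection rate or pilot source is given for it.

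**The concern.** The formula is meant to link sample size to detectable effect. If V is itself built from N, that link is lost, and the result shows only which standard error was assumed. The figure is also attached to the ceiling of 2000, although the study is planned at about 1430.

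This is the protocol's only statement of the effect the study can detect. Section 6 puts both NAFLD status and blood markers into the logistic regression. A single odds ratio cannot describe a yes/no condition and a continuous marker alike. At 1430 it may be too favourable for many yes/no predictors and too cautious for a continuous marker expressed per SD.

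The refinement after 100 participants is also exposed. If V is again defined as se² × N with N as the unknown, N cancels and no sample size can be obtained.

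**Working it through.** **Inputs from section 3.1:** multiplier 8; se = 0.125; V = (se × √N)²; N = 2000 (ceiling) and 1430 (plan); ADR 15% in 1000 non-BCSP patients and 35% in 430 BCSP patients. **From section 1:** "The mean ADR per colonoscopist within the FOBt BCSP is 46.5"%. **Assumed here, because the protocol gives none:** exposure shares of 50%, 25% and 10%, and a variance inflation of 1.5 in one scenario.

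**1. Reproduce the figure.** β² = 8V/N = 8 × se² × N/N = 8 × se². So β = √8 × 0.125 = 0.3536 and OR = exp(0.3536) = 1.424. N has dropped out, and 100, 1430 or 2000 patients all give 1.424. With the exact two-sided multiplier, (1.960 + 0.842)² = 7.85, the result is 1.419. Both round to the stated 1.42.

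**2. Where 0.125 might come from.** For an unadjusted, evenly split yes/no predictor at 15% ADR and N = 2000, se = 1/√(0.15 × 0.85 × 0.25 × 2000) = 0.1252. This fits a standard error that belongs to 2000 patients, but the protocol does not say so. The same predictor at 1430 has se 0.1481 and a detectable OR of 1.52.

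**3. Hold V fixed, taking 0.125 as the standard error at 2000.** V = 0.125² × 2000 = 31.25. At 1430:
- se = √(31.25/1430) = 0.1478
- detectable OR = exp(√(8 × 31.25/1430)) = exp(√0.1748) = 1.519
- power for 1.42 = Φ(ln 1.42/0.1478 − 1.96) = Φ(0.41) = 0.66

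**4. Derive V from the protocol's own rates.** Pooled ADR = (0.15 × 1000 + 0.35 × 430)/1430 = 300.5/1430 = 21.0%. For a yes/no predictor with exposed share f,

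V = 1/[(1−f) p0(1−p0)] + 1/[f p1(1−p1)],

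with p0 and p1 solved so that the overall rate is 21.0% at the odds ratio in question. The detectable OR solves ln OR = √(8V/N). For half exposed at 1430, p0 = 0.180, p1 = 0.241 and V = 24.5, so OR = exp(√(8 × 24.5/1430)) = 1.45.

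| Predictor | OR at 1430 (power for 1.42) | OR at 2000 (power for 1.42) |
|---|---|---|
| 50% exposed | 1.45 (76%) | 1.37 (89%) |
| 25% exposed | 1.50 (68%) | 1.41 (82%) |
| 10% exposed | 1.74 (41%) | 1.60 (54%) |
| Continuous, per SD | 1.20 | 1.17 |

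Simulation (40,000 runs per case) gives power for 1.42 of 77%, 68% and 42% at 1430, and 89%, 82% and 53% at 2000.

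**5. Sensitivity at 1430.**
- With the BCSP rate at 46.5%, the pooled rate is (150 + 200)/1430 = 24.5%. The detectable ORs are 1.42, 1.47 and 1.70, with power for 1.42 of 81%, 73% and 44%.
- With the 21.0% rate and V inflated by 1.5 for correlation among covariates, the detectable ORs are 1.58, 1.63 and 1.94.

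**6. The planned size itself.** 10 × 15/0.15 = 1000 and 10 × 15/0.35 = 428.6, which rounds to the stated 430. The total of 1430 stands and does not use the 1.42.

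**The case against.** V = se² × N is the correct way to turn a standard error at a known N into a per-subject variance. The text names 2000 immediately before the standard error, so the natural reading is 0.125 at 2000. On that reading the calculation is redundant, not wrong, and 1.42 is a fair figure for 2000: the rates in the protocol give 1.37 for half exposed and 1.41 for a quarter exposed. Any power statement assumes a variance. At 1430 the even-split case misses by only about 0.03 in the odds ratio, and the miss disappears with the 46.5% BCSP rate. The larger shortfalls depend on exposure shares and an inflation factor that are not in the protocol. The main aim is a risk model sized by events per variable, so no recruitment number depends on 1.42.

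Much of this stands. The 1.42 is not a slip in the sums, the even split is a near miss, and the sample size is unaffected. It does not rescue the statement. On the natural reading the figure belongs to the ceiling, yet the section says without qualification that the study has sufficient power for it, while planning about 1430 and expecting little change. The same V at 1430 gives 66% power, with no assumption beyond that reading. The other possibility is that 0.125 applies at 1430. Then 1.42 would hold there and 2000 would detect about 1.35, but this conflicts with the sentence that names 2000. Nor can the matter be left to an analysis plan, because the calculation and the power claim are printed in the protocol.

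**Conclusion.** The concern holds and should be fixed. As written, 1.42 follows from se = 0.125 at any N, the 0.125 has no stated basis, and no detectable odds ratio is established for the planned 1430.

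If 0.125 is the standard error at 2000, the detectable odds ratio at 1430 is 1.52 and power for 1.42 is 66%. With V from the protocol's sizing rates, the answer at 1430 depends on the predictor: 1.45 to 1.74 for exposed shares from 50% down to 10%, and about 1.20 per SD for a continuous marker. Those shares are assumptions, and the figures make no allowance for covariate correlation, which would raise them. A higher BCSP detection rate would lower them.

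**What to change.** In section 3.1:

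1. Derive V without using N, from the stated detection rates, an explicit exposure share (or SD) and an allowance for correlation among covariates. For rarer exposures, use the variance at the alternative.
2. Replace the single 1.42 with detectable odds ratios at 1430, and give 2000 as a second scenario. Include at least one yes/no predictor and one continuous marker. If 0.125 is kept, state the predictor, detection rate and N that it comes from.
3. For the refinement after 100 participants, calculate V from their standard error and their n, then hold it fixed while N varies.

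The cost is rewriting one paragraph. No extra patients are needed, and neither the target of 1430 nor the analysis changes. The only drawback is a less favourable stated figure for most yes/no predictors.

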#### 3.2 Inclusion criteria

- 1. Aged 18 years and over
- 2. Able to give informed consent
- 3. Indications:
  - a. Patients with positive faecal occult blood test (FOBt) referred for index colonoscopy as part of Bowel Cancer Screening Programme
  - b. Colonoscopy conversion from Bowelscope
  - c. Index diagnostic colonoscopy due to new gastrointestinal symptoms (including but not restricted to diarrhoea, change in bowel habit, abdominal pain, PR bleeding, weight

loss), iron deficiency anaemia, family history of CRC, abnormal findings on cross sectional imaging

Recruitment materials will be produced in English; however, if language difficulties emerge in an interested patient, a professional translation service specialising in facilitating phone consultations will be used.

#### 3.3 Exclusion Criteria

- 1. Absolute contraindication to colonoscopy
- 2. Unable to give informed consent
- 3. Known colorectal cancer
- 4. Known polyposis syndrome
- 5. Previous total/subtotal colectomy
- 6. Known colonic stricture which would prevent completion of colonoscopy
- 7. Attending for therapeutic procedure
- 8. Attending for assessment of a known lesion
- 9. Attending for assessment of known inflammatory bowel disease (IBD)
- Attending for surveillance colonoscopy (polyp surveillance, post colorectal cancer surveillance, IBD surveillance)
- 11. Colonoscopy within the last 5 years

#### 3.4 Withdrawal Criteria

- 1. New diagnosis of a polyposis syndrome
- 2. Incomplete procedure due to any cause such as colonic stricture or obstructing lesion preventing completion of procedure, withdrawal of consent from patient

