Patients undergoing a colonoscopy usually have an intravenous cannula inserted to allow administration of sedative medication, analgesia and smooth muscle relaxants. Where possible the blood tests will be taken at the time of cannula insertion. To enable this, a size 18G (green) cannula will be used. Where obtaining bloods from the cannula is not possible (failed attempt or poor venous access), this will be done using separate standard venepuncture methods. Blood samples will be collected in the appropriate containers and sent to the clinical laboratory at the site hospital. The blood tests will be requested and labelled according to individual site-specific usual practice. The samples will not be anonymised, to enable the results to be later checked by a research nurse and entered onto the pseudonymised CRF. The samples will be destroyed in line with individual site Trust policy (usually within 3-7 days). Bloods will include:

- 1. Bilirubin
- 2. Alanine aminotransferase (ALT)
- 3. Alkaline phosphatase (ALP)
- 4. Aspartate aminotransferase (AST)
- 5. Gamma-glutamyl transferase (GGT)
- 6. Immunoglobulin A
- 7. Full blood count (FBC)
- 8. HbA1c
- 9. Fasting blood glucose
- 10. Lipids: Cholesterol, HDL and Triglycerides
- 11. Albumin

In the event that haemolysis of LFTs occurs, patients will still be included in the study to allow for analysis of other risk factors and their association with adenomas.

Following colonoscopy to allow completion of the histological dataset, additional information will be collected either at the time of colonoscopy or from hospital reporting systems or from the patient record on the BCSP dataset. These will include:

- 1. Site and number of cancers diagnosed
- 2. Number of adenomas
  - a. Site
  - b. Morphology
  - c. Size
  - d. Villous component
  - e. Degree of dysplasia

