#### 5. Assessment and Follow Up

Clinical follow up will be as per routine clinical practice. Where colonoscopy is incomplete, the reason for this will be recorded. Eligible, consented patients will remain in the study for two weeks following discharge from the endoscopy day ward on the day of their procedure. This is to allow time to collect data from the blood and histology reporting systems. No additional visits are required for patients who enter the study. Any follow up appointments post-colonoscopy will be as per routine care for the unit. The timescale for the out-patient appointment and subsequent care will be unaltered by participation in the study.

Checking liver function tests and HbA1c may pick up new diagnoses of fatty liver disease or diabetes. All abnormal blood tests will be communicated to the participant's GP for further action by a member of the research team.

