#### 6. Statistics and Data Analysis

Data from the CRFs will be transferred to a secure and encrypted electronic computer database. Statistical analysis will be undertaken by [name], Professor of Biological Modelling at Newcastle University.

The relationship between adenoma incidence, NAFLD and blood markers will be investigated using logistic regression whilst adjusting for patient-related demographic variables including age and gender. This will assess the independent contribution of predictors to the odds of adenomas being found. Stepwise removal of non-significant covariates will then be used to identify variables best able to predict adenoma presence. ROC plot and AUC analyses of sensitivity and specificity will be used to characterise the ability of the model to discriminate between patients with and without adenomas and their potential as a predictive tool. These analyses assess the independent contribution of variables to the probability that adenomas will be found, but do not allow for confounding, interaction and associated indirect effects on detection. Structural Equation Modelling (SEM) will be used to investigate impact of indirect and direct effects of the predictors on adenoma incidence. Parsimonious models for logistic regression and SEM will be compared in terms of their ability to predict adenoma presence.

As multiple adenomas may occur, the extent to which adenoma number is related to abnormal liver enzymes using Poisson regression models and SEM will be measured, following the same analytical framework. It is anticipated that the presence of multiple adenomas will be zero-inflated, with some patients having zero and others many. The extent to which zero-inflated models (eg allowing for aggregation) improve the prediction of adenomas will be assessed. Robustness and validation of all models will be validated using bootstrapping. The best model will be developed into a predictive tool.

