#### 8. Study Management

#### 8.1 Data Protection

Patient data will be held on site at the Trust in accordance with local Trust policies. Patients will be assigned a unique study ID at study entry. All data passed to the trial team will have all patient identifiable data removed, aside from the unique study ID. Patients who withdraw will have all data collected up until the point of withdrawal included in the study. This data will be uploaded onto an electronic CRF and included in the analysis of the study. Data will be submitted either directly onto the electronic CRF or onto paper CRF before input into the electronic CRF.

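### Section 3.4 withdraws newly diagnosed polyposis, but section 8.1 keeps the patient's data in the analysis, where one high count can distort the adenoma-number models

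*Protocol*

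**What the plan says.** Section 3.3 of the protocol excludes "Known polyposis syndrome" at entry. Section 3.4, item 1, extends this to cases that come to light during the study: "New diagnosis of a polyposis syndrome" is a withdrawal criterion. Item 2 of the same section lists incomplete procedures and withdrawal of consent.

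Section 8.1 sets one rule for the data of withdrawn patients: "Patients who withdraw will have all data collected up until the point of withdrawal included in the study". It continues: "This data will be uploaded onto an electronic CRF and included in the analysis of the study". No exception is made by reason for withdrawal.

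On timing, section 3.5 says of the polyp and histology data that "additional information will be collected either at the time of colonoscopy or from hospital reporting systems", and the items include "Number of adenomas". Section 5 adds: "Eligible, consented patients will remain in the study for two weeks following discharge from the endoscopy day ward". That period exists so that blood and histology results can be retrieved.

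On use, section 6 says that "the extent to which adenoma number is related to abnormal liver enzymes using Poisson regression models and SEM will be measured". It also foresees zero-inflated models, mentions aggregation, and plans bootstrap validation. It gives no exclusion, cap or sensitivity analysis for polyposis.

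**The concern.** Sections 3.3 and 3.4 together show that patients with a polyposis syndrome are not meant to inform the risk model, and the Background frames the risk factors around sporadic neoplasia. But the findings that would usually prompt a polyposis diagnosis are those of the study colonoscopy and its histology. By then the questionnaire, measurements and bloods will usually have been taken, and some or all of the adenoma count is likely to be available. If section 8.1 is followed literally, withdrawal may take little or nothing out of the dataset.

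What is at stake is the adenoma-number analysis. Adenoma burden is part of the first objective in section 2.1. A count model gives weight to a single extreme value, and an extreme count of hereditary origin would be attributed to whichever liver or obesity group the patient belongs to.

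**Working it through.** **Plan's own figures.** Section 3.1 uses N = 10 × k/p with k = 15.
- Symptomatic (non-BCSP) patients: 10 × 15/0.15 = 1000.
- Screening (BCSP) patients: 10 × 15/0.35 = 428.6, stated as 430.
- Total: 1430, as stated.
- Expected adenoma-positive patients: 1000 × 0.15 + 430 × 0.35 = 150 + 150.5, about 300.

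**Assumptions not in the protocol.** Two adenomas per positive patient, so T = 300 × 2 = 600. One polyposis patient with C = 20, 50 or 100 recorded adenomas. No true association. The group at risk is 25% of patients, close to the obesity prevalence in the Background (24.4% of men, 25.2% of women).

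**Crude rate ratio.** Without the extra adenomas, the 25% group has 150 in 357.5 patients and the rest has 450 in 1072.5, so the ratio is 1.00. Adding C to the 25% group gives RR = 1 + C/150. Adding C to the other group gives RR = 1/(1 + C/450). The naive Poisson standard error of log RR is √(1/a + 1/b), where a and b are the two adenoma totals.

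| C | Share of all adenomas | RR, patient in the 25% group | z | RR, patient in the other 75% | z |
|---|---|---|---|---|---|
| 20 | 20/620 = 3.2% | 1.13 | 1.4 | 0.96 | −0.5 |
| 50 | 50/650 = 7.7% | 1.33 | 3.4 | 0.90 | −1.1 |
| 100 | 100/700 = 14.3% | 1.67 | 6.5 | 0.82 | −2.2 |

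For example, at C = 100 in the 25% group: SE = √(1/250 + 1/450) = 0.079, and ln 1.667/0.079 = 6.5.

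**Sensitivity to T.** With 1.5 to 3 adenomas per positive patient, T runs from 450 to 900. For a patient in the 25% group, RR then runs from 1 + 20/112.5 = 1.18 down to 1 + 20/225 = 1.09 at C = 20. At C = 100 it runs from 1 + 100/112.5 = 1.89 down to 1 + 100/225 = 1.44.

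**Simulation check.** 1000 patients at 15% positive and 430 at 35%, a mean of two adenomas per positive patient, a binary marker with no effect, and adjustment for screening status. Fits were compared with and without one marker-positive polyposis patient.
- Poisson, marker prevalence 20%: the median rate ratio was 1.17, 1.39, 1.83 and 2.67 at C = 20, 50, 100 and 200, against about 1.00 without the patient. Nominal p < 0.05 occurred in 39%, 89%, 100% and 100% of runs, against 17–24% without (the simulated counts are already overdispersed).
- Poisson, C = 100, prevalence 10%, 20% and 30%: median rate ratio 2.66, 1.83 and 1.56.
- Robust standard errors, C = 100: p < 0.05 in about 10%, 2% and 1% of runs at those three prevalences. The point estimate is the same distorted one.
- Negative binomial, prevalence 20%, C = 100: median rate ratio 2.00, with p < 0.05 in 88% of runs against 5% without.
- Logistic model of presence, prevalence 20%, C = 100: odds ratio 0.99 without and 1.01 with the patient. Across all settings run, the median shifted by no more than about 0.04.

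Zero-inflated and structural equation models were not fitted.

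**The case against.** Several points on the other side carry weight.

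- **The clause may mean consent only.** Section 8.1 is a data-protection clause, and section 7.2 speaks of the participant's right to withdraw. One could read 8.1 as covering patients who choose to leave, with 3.4(1) removing ineligible ones. But 3.4 puts polyposis and withdrawal of consent under one heading, and 8.1 draws no distinction. The reading is possible; the text does not settle it.
- **The count may be incomplete.** The protocol does not date the polyposis diagnosis. If it is made on sight, histology may be pending. Section 3.1 follows up polyps that are detected and removed, and section 3.5 takes the polyp details of anticoagulated patients from a second colonoscopy. A reader might infer that the full count is always on file at withdrawal; the protocol does not say so. Under 8.1, however, inclusion would then depend on the timing of the diagnosis, which is no better.
- **Section 6 has safeguards.** It mentions aggregation as well as excess zeros, and bootstrapping. Bootstrapping may reveal the instability, and robust errors would curb false significance. Neither removes a patient whom the protocol does not want, and the negative binomial estimate was also distorted at 100 adenomas.
- **An analysis plan could define the analysis sets.** It could, but the protocol has already fixed the rule, and a plan that left these patients out would depart from 8.1 as written.

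**Conclusion.** The point holds as a conflict between sections 3.4 and 8.1 that can distort the adenoma-number analysis. On the assumptions above, the effect is modest at about 20 recorded adenomas (RR 1.13 or 0.96, neither nominally significant) and material at about 100 (RR 1.67 or 0.82). It is larger for smaller marker groups. Whether any such patient will be recruited, and with what count, cannot be read from the protocol. Nor does the protocol limit the term to adenomatous syndromes.

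Two stronger readings are tempting and are not supported. A reader might infer that a single such patient makes any group look highly significant. That fails at 20 adenomas. Even at 100, a patient in the larger group gives only z = −2.2, and the z of 6.5 depends on the naive Poisson standard error. A reader might also infer that the whole risk model is compromised. The logistic model of adenoma presence, which section 6 describes first, barely moves. The exposure is confined to the models of adenoma number; its size in the zero-inflated and structural equation models is untested.

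**What to change.** Reconcile sections 3.4 and 8.1 with a sentence or two:
- Participants withdrawn under 3.4(1) are reported in the participant flow but excluded from the adenoma models, consistent with exclusion criterion 4. This matters for the adenoma-number models; applying it to the presence model as well keeps one analysis population.
- The 8.1 rule on including data collected before withdrawal does not apply to these participants.
- The exclusion covers diagnoses known to the study team from the data it routinely collects. No extra follow-up is added, since sections 3.1 and 5 require none beyond routine care.

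The cost is the wording and an exclusion flag in the dataset. The downside is the loss of at most a few participants whom the protocol already intends to remove. The change concerns data handling only and does not touch clinical care.
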